## 9.2 POPULATIONS FOR ANALYSES

Our population for analysis is prescribers of DOACs for ambulatory patients. All eligible participants will be randomized. (Randomization by prescriber, not by patient.) All randomized participants who received an intervention will be included in safety analyses. All analyses, primary or secondary, will be reported by sex/gender and race/ethnicity as reported in the EHR.

## 9.3 STATISTICAL ANALYSES

### 9.3.1 GENERAL APPROACH

The main effect analyses will allow us to determine the impact of different alert- and notification types on evidence-based DOAC prescribing in both newly prescribed DOAC prescriptions and existing DOAC prescriptions in order to understand under what contexts prescriber-pharmacist collaboration is an effective implementation strategy. In both our primary and secondary outcomes, our analyses will compare the main effects of each intervention, i.e., new prescription alerts (Alerts 1 vs 2) and existing-prescription notifications (Notifications A vs B), to determine which are most effective. For both interventions, the outcome of interest will be whether the patient whose prescription triggered the alert/notification (i.e., is receiving a non-evidence based DOAC) has their prescription changed following the alert or notification.

For the primary intervention outcome (existing-prescription notifications), main effect analyses will compare the proportion of patients receiving an evidence-based DOAC prescription within seven business days following the notification between prescribers randomized to receive the notifications themselves vs. prescribers for whom notifications were sent directly to anticoagulation clinic pharmacists.

For the secondary intervention outcome (new DOAC prescription alerts), main effect analyses will compare the proportion of patients receiving an evidence-based DOAC seven business days following the notification between prescribers randomized to receive enhanced alerts vs. enhanced alerts plus pharmacist referral.

The treatment interaction will allow evaluation of whether certain alerts and notifications work better when provided in tandem.

The main outcome analysis will use mixed-effects logistic regression models to account for the binary patient-level outcome variable of evidence-based DOAC receipt after an alert. The two treatment factors and their interaction will be included as fixed effects, as well as any stratification variables and baseline patient- and/or prescriber-level characteristics that are unbalanced. A prescriber-level random effect will account for patient clustering within prescribers, and an unstructured covariance matrix will be used for residual errors. Similar mixed-effects regression analyses will be conducted for secondary outcomes, adapted for different outcome measures or levels of analysis.

**Missing Data.** Patients will contribute primary outcome data through EHRs as long as they stay with Michigan Medicine. Patient attrition due to leaving Michigan Medicine also discontinues the ability for their Michigan Medicine prescribers or pharmacists to affect their medication prescription, so does not induce missing data under intent-to-treat principles. Similarly, data on prescribers (e.g., secondary outcome/process data) will continue to be captured via EHR as long as they are employed at Michigan Medicine. Prescribers that leave Michigan Medicine during the study will be lost to follow-up; however, the Michigan Medicine prescriber population (attending physicians, nurse practitioners, and physician assistants) is generally quite stable and, given the nature of the intervention, we expect attrition to be entirely unrelated to treatment assignment. House officers, while less stable in longevity, do have predictable start and stop dates for patient care, such that missingness is predictable and not related to

treatment. Proposed mixed-effects analyses produce valid inferences for data that is missing at random, and multiple imputation will be used as appropriate. If multiple imputation is employed, all analyses will be performed with and without imputed data. Further sensitivity analyses will evaluate robustness of results under informative missingness scenarios, as appropriate.

---

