## 4 STUDY DESIGN

### 4.1 OVERALL DESIGN AND SCIENTIFIC RATIONALE

This prospective randomized clinical trial will determine the effectiveness of alerts (for newly prescribed DOAC) and notifications (for existing prescriptions) in reducing prescription errors. We have two central hypotheses: (1) alerts and notifications will reduce prescription errors; and (2) involving pharmacists in the prescribing process through alerts and notifications will increase the efficacy of the alerts and notifications. These two hypotheses will be evaluated by the proportion of prescriptions that are changed following an alert (for a new prescription) or notification (for an existing prescription).

This study is 18-month prospective, randomized, controlled clinical trial of medication alerts and notifications in the ambulatory settings. See section 1.2 for an overview of the schema. Prescribers will be randomized into one of four conditions upon triggering a DOAC alert or notification (see figure 4.1-1, below).

[figure not shown]

Figure 4.1-1: Timeline of trial protocol.

Alert styles 1 and 2 (for newly prescribed DOACs) will differ only in the inclusion or exclusion of a pharmacy consult (i.e. there will or will not be an option to click to automatically receive a consult). Notifications (for existing DOAC prescriptions) will differ in that the notification will either be routed directly to the pharmacist, who will then consult the prescriber if need be, or be routed to the prescriber directly.

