## 9 STATISTICAL CONSIDERATIONS

### 9.1 SAMPLE SIZE DETERMINATION

This study is powered for our primary comparison, which is the comparison of our two different notifications. We will use mixed-effects binary logistic regression to model the proportion of inappropriate DOACs that are changed within 7 days following an alert.

We anticipate randomizing 300 prescribers to different notifications over the course of the study, allowing for a main effect comparison of 150 prescribers randomized to each of Notification A vs. B. This estimate for prescribers is pulled from 2019 preliminary data indicating Michigan Medicine had more than 1000 unique DOAC prescribers, and a one-day pull in February 2020 that indicated more than 250 prescribers on that day had one or more patients currently receiving an inappropriate DOAC, thus eligible for randomization to a longitudinal notification. For our secondary aim, examining the main effect of alerts, we also anticipate randomizing 300 prescribers to initial prescription alerts over the study period, or 150 to each of Alert 1 and Alert 2, respectively.

For our patient-level main effects analyses, we estimate that prescribers will average 2 patients that trigger an inappropriate DOAC alert over the 12-month trial period. As of June 14, 2022, Michigan Medicine currently has 11,590 patients receiving a DOAC. Pilot data indicates that about 40% of prescribers changed prescriptions following an notification that did not involve a pharmacist; notifications that did involve pharmacists resulted in change approximately 60% of the time. Using a base rate of 40% and assuming a patient  $n=600$ , alpha of 0.05 and prescriber-level ICC of 0.1, we will have 80% power to detect a difference in proportions of 0.12 (or 40% vs. 52%). Table 3 shows power for several other risk ratios, baseline rates, and number of patients per prescriber. All estimates were computed in Stata 17.

Table 3. Power Calculations (Prescriber N=300)

Table 3. Power Calculations (Prescriber N=300)				
Patient n=2	Base Proportion			
Risk Ratio	0.3	0.4	0.5	0.6
1.2	32%	47%	65%	84%
1.3	44%	63%	83%	96%
1.4	67%	87%	98%	>99%
1.5	84%	97%	>99%	>99%
1.6	94%	>99%	>99%	>99%
Patient n=3				
Risk Ratio				
1.2	42%	60%	79%	94%
1.3	74%	91%	99%	>99%
1.4	93%	>99%	>99%	>99%
1.5	>99%	>99%	>99%	>99%
1.6	>99%	>99%	>99%	>99%

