#### **Sensitivity analyses.**

**Carryover effects for new-prescription alerts:** Primary analyses will be conducted as intent-to-treat analyses among prescriber-patient dyads for whom an alert was triggered. This allows investigation of the best types of alerts given the need for an alert. However, for new-prescription alerts, it is also possible that alerts that include the option for pharmacist referral vs. those that don't also differentially affect how many future DOAC prescribing errors are made. Specifically, prescriber-pharmacist collaboration may provide the prescriber with new knowledge about evidence-based DOAC prescribing that could be applied to future DOAC prescriptions, avoiding the occurrence of an alert altogether. To

explore these effects, we will also evaluate the main effect of the two new-prescription alerts on the proportion of DOAC patients that receive a new prescription for an evidence-based DOAC using the model described above, but including all patients to whom they prescribed a DOAC from the point they received their first new-prescription alert through the end of the 18-month study period. This will allow us to evaluate whether correct DOAC prescribing improved overall by type of new-prescription alert.

**Treatment-as-received analyses:** In line with intent-to-treat clinical best practices, prescribers will be randomized to both types of alerts at the time of their initial receipt of either type of alert. This approach was chosen for both good clinical practice and pragmatic reasons, but also with the support of our preliminary data, which showed that on one day, more than 1/4 of Michigan Medicine prescribers had one or more DOAC patients receiving a non-evidence-based prescription (see Power and Sample Size, above). There is a possibility that during trial period, some prescribers will only ever receive one type of alert, never exposed to their second randomized treatment—i.e., they made an initial prescribing error but never had a DOAC-receiving patient need a change in prescription, or vice versa. While we believe that this will be the case for only a minority of enrolled prescribers, sensitivity analyses will examine treatment-as-received effects and will re-assess main effects for the two factors including only patients for prescribers who received that type of alert.

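### The primary model in Section 9.3.1 does not guarantee the Notification A vs B main effect that was powered, and two of its rules (residual covariance, covariates chosen by imbalance) are faulty

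*Combined protocol and SAP*

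**What the plan says.** Section 9.1 describes the design as "allowing for a main effect comparison of 150 prescribers randomized to each of Notification A vs. B". It names the method as follows: "We will use mixed-effects binary logistic regression to model the proportion of inappropriate DOACs that are changed within 7 days following an alert". No interaction is mentioned there.

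Section 9.3.1 repeats that main effects are compared, and Section 9.3.2 refers back to it for the primary outcome. The model in 9.3.1 is therefore the only one given. It has these parts:

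- Fixed effects: "The two treatment factors and their interaction will be included as fixed effects", plus the stratification variables and "baseline patient- and/or prescriber-level characteristics that are unbalanced".
- A prescriber-level random effect for clustering.
- A further clause: "an unstructured covariance matrix will be used for residual errors".

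The interaction has its own stated purpose, which is to see whether particular alerts and notifications reinforce each other.

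The allocation is described in four ways:

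- Section 4.1: "Prescribers will be randomized into one of four conditions upon triggering a DOAC alert or notification".
- Section 9.3.5, treatment-as-received paragraph: "prescribers will be randomized to both types of alerts at the time of their initial receipt of either type of alert".
- Section 1.2: a prescriber may be in one of the two components or in both.
- Section 6.3: alert vs notification is listed as a randomization stratum, beside the trainee/specialist/primary-care stratum.

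**The concern.** Three features of the model leave the primary analysis open or unworkable.

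**(a) The contrast is not named.** In a model with two factors and their product, the coefficient labelled notification depends on the coding. With 0/1 coding it is the A-vs-B effect in the reference alert arm only. With centred (effect) coding, or a contrast averaged over alert arms, it is the main effect that Section 9.1 powers. Two analysts who both follow 9.3.1 could run different primary tests, and the choice could be made after the data are seen.

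**(b) The residual covariance does not exist in this model.** Given the random intercept, a binary outcome has a variance fixed by its mean, so no free residual matrix is left to estimate. Something similar can be set up as a working covariance under pseudo-likelihood or GEE, but that is a different method. Patients of one prescriber also have no common order or number with which to index such a matrix.

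**(c) Covariates are chosen by observed imbalance.** There is no list, criterion or threshold. Under randomization, baseline imbalance is chance, so the rule makes the model depend on the data. In logistic regression, each added prognostic covariate also changes the conditional odds ratio being estimated.

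**Working it through.** **Inputs (Section 9.1):** 300 prescribers, 150 per notification arm; 2 patients each on average; ICC 0.1; alpha 0.05; 40% vs 52%; stated power 80%. The test is taken as two-sided. Section 9.1 says so only for the moderator analyses, but two-sided reproduces the stated figure (one-sided would give 88.0%).

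**Step 1: reproduce the plan's figure.**
- Design effect = 1 + (2 − 1) × 0.1 = 1.1. Effective n per arm = 300 / 1.1 = 272.7.
- Null SE = √(2 × 0.46 × 0.54 / 272.7) = 0.0427. Alternative SE = √((0.24 + 0.2496) / 272.7) = 0.0424.
- z = (0.12 − 1.96 × 0.0427) / 0.0424 = 0.86, so power = 80.5%. The difference detectable with 80% power is 0.119.

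The stated 80% is reproduced. Table 3 prints 63% for the same case (2 patients, base 0.4, risk ratio 1.3). That is a separate inconsistency; the text's figure is the one used here.

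**Step 2: 0/1-coded coefficient with the interaction in the model.** Only prescribers in the reference alert arm inform this coefficient, which is half of the 300 if the alert factor is allocated equally.
- Effective n per notification arm = 150 / 1.1 = 136.4. SEs 0.0604 and 0.0599.
- z = (0.12 − 1.96 × 0.0604) / 0.0599 = 0.03, so power = 51.1%. The detectable difference is 0.169.

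**Step 3: main effect averaged over alert arms, same model, log-odds scale.** Assume four equal cells and no true interaction.
- Log odds ratio = logit(0.52) − logit(0.40) = 0.4855 (odds ratio 1.625).
- Cell variances = 1 / (136.4 × 0.24) = 0.0306 and 1 / (136.4 × 0.2496) = 0.0294.
- SE within one alert arm = √(0.0306 + 0.0294) = 0.245. Power = Φ(0.4855 / 0.245 − 1.96) = 50.9%.
- SE averaged over alert arms = ½√(2 × 0.0306 + 2 × 0.0294) = 0.173. Power = Φ(0.4855 / 0.173 − 1.96) = 80.1%.

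**Step 4: simulation check.** 500 replicates; beta-binomial data with ICC 0.1 and no true interaction; exchangeable GEE logistic model as a stand-in for the mixed model; Monte Carlo SE about 2 points.

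| Test of A vs B | Rejection rate |
|---|---|
| Notification factor only | 78.4% |
| Effect-coded, with interaction | 78.6% |
| 0/1-coded, with interaction | 51.8% |

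So the interaction term itself costs nothing. What matters is which contrast is read.

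**Step 5: sensitivity.** With 3 patients per prescriber, power is 91.1% for the main effect and 64.6% within one alert arm. At the pilot difference of 40% vs 60% it is 99.7% and 91.5%. Power for the interaction itself is low: a difference of differences of 0.12 has twice the main-effect SE, so power = Φ(0.12 / (2 × 0.0424) − 1.96), about 29%.

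**Step 6: dependence on allocation.** The interaction model needs an alert assignment for every notification prescriber. Only the 9.3.5 text clearly secures that. If just 75% or 50% had one (assumed shares) and the rest dropped out of the model, power for A vs B would be 68% or 51%.

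**Step 7: covariate screening, illustrative only.** If 6 to 12 independent characteristics were each screened at 5%, at least one would be flagged by chance in 1 − 0.95⁶ = 26% to 1 − 0.95¹² = 46% of trials. The documents give neither the number of characteristics nor a screen. This shows how often the rule would act, not a bias or an error rate.

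**The case against.** The strongest reply is that the plan says what it tests. Sections 9.1, 9.3.1 and 9.3.2 all name the main effect of the notification factor, and the interaction has a separate stated purpose. No section specifies 0/1 coding or makes a reference-level coefficient the primary test. Read that way, power is about 80% with the interaction in the model. This stands: a reader might infer that the model fails to deliver the powered comparison or cannot be fitted, and the documents do not support that. They leave the contrast unnamed, which is a lesser fault.

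A reader might also infer from Section 4.1 that the 300 prescribers are divided among four exclusive conditions, so that nobody holds both factors and the notification comparison is halved. The documents do not support this either. Section 9.1 plans 300 prescribers for notifications and 300 for alerts, and Section 1.2 allows both. The four conditions can be the four cells of the two-by-two allocation in 9.3.5. The figure that 4.1 refers to is not available here.

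On covariates, Section 6.3 blinds the study team to condition during analysis, which limits deliberate steering. It does not remove the problem, because coded arm labels are enough to see which characteristics differ and the model is still settled after that look. Adjusting for the stratification variables is proper and is not criticized.

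The residual clause is fairly called a drafting error with no computable consequence. It still cannot be carried out as written.

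**Conclusion.** The point holds as a fault of specification and should be fixed before analysis. The primary test is not uniquely defined. Depending on the contrast read, power for 40% vs 52% is about 80% or about 51%, with a detectable difference of about 12 or about 17 points. The lower figures apply only if a 0/1-coded coefficient is taken as primary. They assume 2 patients per prescriber, ICC 0.1, a two-sided 5% test, equal allocation of the alert factor and an alert assignment for every notification prescriber.

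The residual covariance clause and the imbalance rule are wrong in themselves, but no loss of power can be attached to either from the documents.

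**What to change.** - **Primary test.** Name the Notification A vs B main effect as the single primary test. Use either a main-effects model, or effect coding or averaging over alert arms if the interaction is kept. State the coding. Make the interaction a secondary test.
- **Covariance.** Delete the residual covariance clause and keep the prescriber random intercept.
- **Covariates.** Replace selection by imbalance with the randomization strata plus a fixed list from the baseline variables already named for the moderator analyses in 9.3.5: age, VTE vs AF, number of concurrent medications, creatinine clearance, and DOAC prescribing volume in the six months before randomization.
- **Allocation.** Reconcile Sections 1.2, 4.1, 6.3 and 9.3.5 with the allocation actually implemented, and say how a notification prescriber without an alert assignment enters the model.

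The cost is text in 9.3.1 and the allocation sections, and a check of how randomization was programmed. The one downside is that the interaction becomes secondary. Little is lost, given its power of about 29% for a 12-point interaction.

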For our secondary prescriber-level outcomes, we will have 94% power to detect a difference in proportions of 0.4 to 0.6. For longitudinal outcomes (e.g., maintenance), this calculation is conservative as it does not account for repeated measures. For our clinical effectiveness secondary outcome, we will have 63% power to detect a difference of 1% vs. 0.5% in adverse event rates for each factor, again assuming 300 prescribers with an average of 2 patients each, and assuming a prescriber-level ICC of 0.03 (for clinical adverse events). A less conservative estimate of 3 patients per prescriber increases this power to 79%

For our exploratory moderation analyses, described below in Section 9.3.5, again assuming 300 prescribers with 2 patients each and an ICC of 0.1, we will have 80% power to detect a minimum effect size of 0.34 for our binary prescriber-level moderators, using a two-sided test with  $[\alpha] = 0.05$ . If our average number of patients per prescriber is 3, this minimum detectable effect size decreases to 0.29 under the same assumptions. For our binary cross-level (patient-level) moderators, assuming a non-randomly varying slope, with an average of 2 patients per prescriber, we will have 80% power to detect a minimum effect size of 0.34; assuming 3 patients per prescriber decreases this minimum detectable effect size to 0.27. Minimum detectable effect sizes for cross-level moderators that also include a random slope are slightly larger at 0.36 and 0.28 respectively

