### 9.3.4 ANALYSES OF IMPLEMENTATION

**Reach:** To assess reach, we will examine the proportion of patients on DOACs that had alerts or notifications fire, as well as the proportion of prescribers that received alerts and/or notifications. To further understand reach, we will also report the proportion and clinical predictors of prescribers who dismissed alerts or notifications (defined as no action within seven calendar days). We will also identify the proportion and predictors of prescribers who used anticoagulation clinic pharmacist referrals in new-prescription alerts. We will also categorize all DOAC alerts based on prescriber and patient characteristics (e.g., demographics, comorbidities).

**Effectiveness:** Analysis of Effectiveness will be the focus of the primary and secondary outcome measures (as noted above). We will evaluate the effectiveness of our DOAC alert system components by examining patient-level clinical adverse event rates (bleeding and thrombotic) within 30 days of triggering the alert. This time period was selected to minimize potential contamination from the safety review mechanism described above, and we recognize that rates for the adverse events will be low.

However, as a T4 implementation study, the primary goal is implementing the evidence-based practice for which efficacy is already established. Supplementary analyses will also examine the effect of the alert system overall on adverse events.

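### At the printed adverse-event rates, the mixed-effects model carried over to secondary outcomes would usually fail, and the plan names no sparse-data method

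*Combined protocol and SAP*

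**What the plan says.** All references are to the combined protocol and SAP.

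- **Section 9.3.1** describes the main outcome model as mixed-effects logistic regression: "The two treatment factors and their interaction will be included as fixed effects, as well as any stratification variables", plus unbalanced baseline characteristics and a prescriber-level random effect. For other outcomes it adds: "Similar mixed-effects regression analyses will be conducted for secondary outcomes, adapted for different outcome measures or levels of analysis".
- **Section 9.1** calls 30-day adverse events the clinical effectiveness secondary outcome and states: "we will have 63% power to detect a difference of 1% vs. 0.5% in adverse event rates for each factor". The inputs are 300 prescribers, 2 patients each and an ICC of 0.03. With 3 patients per prescriber the stated power is 79%.
- **Section 9.3.4** (Effectiveness) compares bleeding and thrombotic events within 30 days and concedes: "we recognize that rates for the adverse events will be low". It names no exact, penalised or reduced model and no rule for non-convergence. Section 8.1 is equally silent.
- **Section 9.3.6** presents adverse events by randomization group descriptively. It also mentions a p<0.01 comparison between arms that may lead to action at DSMB review.

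**The concern.** The model in 9.3.1 has at least six fixed parameters: an intercept, two factors, their interaction, and two terms for the three prescriber strata of Section 6.3. Imbalance covariates and a variance component come on top. The printed adverse-event rates imply fewer than five events.

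If one of the four treatment cells has no event, the interaction log-odds has no finite maximum-likelihood estimate. If a whole arm has none, the main effect has none either. Software may still print very large odds ratios with Wald p-values that mean nothing. Without a named alternative, the analyst would have to pick a replacement model after seeing sparse data by arm. At stake is the inferential comparison of bleeding and thrombosis between arms that Section 9.1 sets out to power.

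**Working it through.** **Inputs.** Section 9.1 supplies the rates (1% vs 0.5%), 300 prescribers split 150 and 150 on each factor, m = 2 or 3 patients each, and ICC 0.03. Alpha is given for the primary calculation ("alpha of 0.05 and prescriber-level ICC of 0.1"), and two-sided testing for the moderation analyses; I assume both apply here. An equal split into four cells of 75 prescribers is also my assumption.

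**Step 1: the plan's own power figures.** Effective n per arm is 150m/(1 + (m−1) × ICC). For adverse events this is 300/1.03 = 291.3 at m=2 and 450/1.06 = 424.5 at m=3. Power = Φ{[|p1−p2|√n − 1.96√(2p̄q̄)] / √(p1q1+p2q2)}.

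- Check on the primary calculation: 40% vs 52%, ICC 0.1, m=2 gives 80.5% (stated 80%).
- Check on the prescriber-level calculation: 0.4 vs 0.6, n=150 per arm gives 93.8% (stated 94%).
- Adverse events, 1% vs 0.5%, m=2: (0.005×17.07 − 1.96×0.1220)/0.1220 = −1.26, so power is 10.4% (stated 63%).
- The same at m=3: power is 13.2% (stated 79%).
- Variants do not rescue the stated figures. A one-sided test gives 17% and 21%; no design effect, 10.6% and 13.8%; 300 prescribers per arm, 17% and 22%.
- 10% vs 5% with the same inputs gives 63.0% and 79.1%, matching both stated figures.

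**Step 2: expected events at the printed rates.** At m=2: 300×0.01 + 300×0.005 = 4.5, or 1.5, 1.5, 0.75 and 0.75 per cell. That is 4.5/6 = 0.75 events per fixed parameter before any covariate. At m=3: 6.75 events.

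**Step 3: chance of empty cells and arms** (independent binomials, one factor active).

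| | m=2 | m=3 |
|---|---|---|
| At least one empty cell | 1 − (1−0.99^150)²(1−0.995^150)² = 83% | 1 − (1−0.99^225)²(1−0.995^225)² = 63% |
| An empty arm of the tested factor | 1 − (1−0.99^300)(1−0.995^300) = 26% | 1 − (1−0.99^450)(1−0.995^450) = 11% |

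Allowing for clustering (beta-binomial, ICC 0.03) changes these little: 84% and 65% for a cell, 28% and 12% for an arm. At m=2 the empty-cell figure is 63% if all cells run at 1%, and 93% if both factors halve the risk.

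**Step 4: the random effect.** Its variance is informed by prescribers with two events. At an average rate of 0.75% and m=2, the expected number is 300×[0.0075² + 0.03×0.0075×0.9925] = 0.08. No such prescriber occurs in about 92% of trials.

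**Step 5: fitting the model.** I simulated 600 trials per scenario and fitted the four-cell random-intercept logistic model by maximum likelihood, without strata or covariates.

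| Scenario | Finite interaction | Finite, and variance estimate off the boundary |
|---|---|---|
| 1% vs 0.5%, m=2 | 17% | 2.5% |
| 1% vs 0.5%, m=3 | 33% | 10% |
| 1% vs 0.5%, m=4 (assumed pooling of alert and notification patients) | 55% | 22% |
| 10% vs 5%, m=2 (about 45 events) | 100% | 62% |

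**The case against.** **The plan does not prescribe the interaction model for adverse events.** A reader might infer that it does. But 9.3.1 ties that model to the main outcome, lets secondary analyses be adapted, and describes the comparisons as main effects. Section 9.1 powers adverse events "power to detect a difference of 1% vs. 0.5% in adverse event rates for each factor". A single-factor model is consistent with all of this, so the point stands as a limit. It does not close the gap, because no simpler model is named. The outcome is also binary and patient-level like the primary one, so neither stated reason for adapting clearly applies. A single-factor fit still meets an empty arm in 26% (11%) of trials.

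**Saying that the model cannot be fitted would be too strong.** Failure is likely, not certain: a finite interaction estimate appears in about one trial in six at m=2 and one in three at m=3.

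**Numbers may be larger than the base case.** Section 9.1 counts 2 patients over 12 months, whereas the trial runs 18 months. The synopsis calls 300 prescribers a minimum, and events are counted after alerts and after notifications. This lowers the risk without removing it. Under the assumed pooling (4 patients per prescriber, 9 events), 45% of simulated trials still had no finite interaction estimate.

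**Harm by arm would still be reported.** A reader might infer that this is the trial's only such comparison. Section 9.3.6 gives counts and proportions by group and a p<0.01 trigger, and Section 10.1.6 gives the DSMB safety data by arm. This stands: the inferential comparison is what could fail.

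**The outcome's standing is modest.** Adverse events are missing from the endpoint lists in Sections 1.1 and 3 and from 9.3.3. Section 9.3.4 puts implementation goals first. Still, 9.1 calls the outcome secondary, and 8.1 places it under its secondary heading.

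**The rates are in doubt.** At 10% vs 5% an empty cell occurs in about 0.1% of trials. That these rates were intended is an inference from the arithmetic; the documents nowhere state them.

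**Conclusion.** The concern holds in this form: at the printed 1% vs 0.5%, a model built like the one in 9.3.1 would usually give infinite or unusable estimates for 30-day adverse events, and the plan names no alternative although it expects low rates. The size is an empty cell in about 83% of trials at 2 patients per prescriber and 63% at 3, and an empty arm in about 26% and 11%.

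This rests on an equal four-way split, on only one factor affecting risk, and on the printed rates being the intended ones. The last is the weakest assumption, because those rates contradict the power stated beside them. If the true rates were near 10% and 5%, the treatment terms could be estimated. Even then, about 45 events over six parameters is 7.5 each, and the variance estimate was off its boundary in only 62% of simulated fits. The documents do not support reading the plan as mandating an impossible model, or as leaving harm by arm unreported. The primary analysis is unaffected.

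**What to change.** 1. **Reconcile Section 9.1 first.** State which adverse-event rates are meant and give the power that follows from them.
2. **Name the analysis in 9.3.4.** Analyse the 30-day outcome one factor at a time, without interaction or imbalance covariates. Report counts and the risk difference with a score-type (Miettinen-Nurminen) or exact 95% interval, as estimation.
3. **Keep the clustering.** Randomization is by prescriber, so inflate the variance using the plan's ICC of 0.03 and the observed cluster sizes. With exactly 2 patients each the design effect is 1.03. The snapshot in Section 2.1 is skewed (median 2, IQR 1–5; mean 670/250 = 2.7), so it may be larger. For example, a patient-weighted mean size of 5 (an assumption) gives 1 + 4×0.03 = 1.12. A prescriber-level bootstrap cannot do this job, because an arm with no events has none in every resample.
4. **Sensitivity analysis.** Use Firth-penalised logistic regression or a prescriber-level permutation test.
5. **Gate the full model.** Fit the 9.3.1 model only if a minimum total number of events, fixed before unblinding, is reached. Any threshold is a convention, so what matters is stating it in advance.

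The cost is one SAP paragraph and a corrected power statement, with no new data. The downside is that no interaction or covariate-adjusted estimate for adverse events is available when events are few.
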